#### **7.2.2.4 Graft Harvest Site Pain**

Since AMPLEX subjects will not undergo graft harvest, this is a patient reported outcome that is applicable to ABG subjects only. Subjects in the ABG group will be asked to assess the pain associated with their graft site. ABG subjects will assess the pain using a VAS. Subjects will mark the location on a 100-millimeter line corresponding to the amount of pain they experienced with 0 mm being “no pain” and 100 mm being “the worst pain imaginable”. This questionnaire will be completed at 2, 6, 12, 24 and 52 weeks after surgery. The assessment and its instructions for use will be provided in the SRM.

### **7.3 Other Assessments**

#### **7.3.1 Concomitant Medications**

At all study visits, subjects will be instructed to report any medications used to treat them over the course of the study.

#### **7.3.2 Vital Signs**

Vital signs will be performed at all study visits. On the day of Treatment, vital signs must be performed prior to surgery. Weight, height and BMI will be performed at screening (Visit 1).

#### **7.3.3 Clinical Laboratory Testing**

Routine clinical laboratory tests (hematology and chemistry, including AST, ALT, ALP, GGT, bilirubin and hemoglobin A1c levels), will be performed at screening (Visit 1) and follow-up through 12 weeks. All female subjects of childbearing potential will have urine pregnancy tests performed at the screening (Visit 1) and within 24 hours of the procedure (Visit 2). At the discretion of the Investigator, additional blood samples may be taken for safety reasons to analyze other clinical laboratory endpoints. All blood samples will be analyzed by a central laboratory. Full details regarding sample collection, processing and shipping will be provided in the SRM. The lab results/reports will be provided to the site. If a laboratory result is abnormal, the Investigator will assess if it is clinically significant (CS) or not clinically significant (NCS). Clinically significant laboratory abnormalities are defined as abnormal results requiring treatment or medical intervention and should be recorded as adverse events. The severity of a clinically significant laboratory finding should be recorded as described; however, abnormal laboratory observations classified as NCS do not require an adverse event to be filed.

### **7.3.3.1 Standard Urinalysis**

Dipstick urinalysis tests will be performed at screening (Visit 1), to assess blood, leukocytes, pH, specific gravity, nitrite, protein, glucose and urobilinogen. If dipstick urinalysis results are positive for blood, leukocytes or nitrite, microscopic urinalysis will be performed.

### **7.3.3.2 Immunological Testing for HBV, HCV and HIV**

Serological testing for HBV, HCV and HIV will be performed at screening (Visit 1). Negative results are required for study admission.

### **7.3.4 Antibody Monitoring**

The presence of anti-B2A antibodies will be evaluated using a tiered approach consistent with FDA guidance. This evaluation consists of screening and confirming for B2A-specific antibodies with use of a ligand binding immunoassay. Following confirmation of the “positive” screening result an antibody titer will be determined. Subsequently, in confirmed anti-B2A antibody positive samples the BMP-2 cross-neutralization potential will be determined by a cell-based assay. Blood for immunogenicity testing will be collected at pre-operative/ screening visit, at 6 weeks and at 12 weeks after surgery. For subjects testing positive for antibodies to B2A, additional blood samples will be obtained at each subsequent follow-up visit and analyzed until antibody titers return to baseline or until the end of the study. Samples will be analyzed at a GLP-compliant laboratory under the responsibility of the Department of Bioanalysis, IPC, Ferring Pharmaceuticals A/S.

### **7.4 Human PK Assessment**

A Pharmacokinetic (PK) assessment will be conducted in a sub-set of subjects to assess the amount of B2A in blood (plasma). Blood for assessment will be collected pre-procedure (baseline) and after surgery on Days 1, 2, 4, 7, and 15. Visit 3 will also consist of Days 2, 4 and 7, for which there will be an **option for blood to be collected at home by a mobile laboratory unit**. From the plasma concentration-time data of B2A, the following parameters will be estimated, if possible: AUC, AUCt, % AUC extrapolated, Cmax, Tmax, t1/2, lambda z, CL/F, Vz/F. The sub-set of subjects will include up to approximately 30 AMPLEX subjects, allowing pharmacokinetic evaluation in at least 20 AMPLEX subjects. Both genders will be represented. Subjects included in the PK sub-set will provide written informed consent prior to the fusion procedure.

## 8 ADVERSE EVENTS

### 8.1 Definitions

An adverse event (AE) is any untoward medical occurrence in a subject participating in a clinical trial. It includes:

- Any unfavorable and unintended sign, symptom or disease temporally associated with the use of the investigational device or control material, whether or not considered to be caused by the investigational device or control material
- Adverse events commonly observed and adverse events anticipated based on the effect of the investigational device or control material
- Any laboratory abnormality, vital sign or finding from physical examination assessed as clinically significant by the Investigator
- Any accidental injuries, reasons for any medical, nursing or pharmacy consultation, or reasons for admission to hospital or surgical procedures

A Serious Adverse Event (SAE) is defined as any AE that:

- ◆ Results in death
- ◆ Is life threatening (the subject is at immediate risk of dying from the adverse experience)
- ◆ Results in subject hospitalization or prolongs existing hospitalization
- ◆ Results in persistent or significant disability/incapacity
- ◆ Is a congenital anomaly/birth defect
- ◆ Is an important medical event that may not result in death, be life-threatening, or require hospitalization may be considered a serious adverse device effect when, based upon appropriate medical judgment, they may jeopardize the subject or subject and may require medical or surgical intervention to prevent one of the outcomes listed in this definition

An unanticipated adverse device effect (UADE) is defined as any serious adverse effect on health or safety or any life-threatening problem or death caused by, or associated with, graft material (either AMPLEX or ABG in the context of this protocol), if that effect, problem, or death was not previously identified in nature, severity, or degree of incidence in the investigational plan or application (including a supplementary plan or application), or any other unanticipated serious problem associated with a medical device that relates to the rights, safety, or welfare of subjects.

An anticipated adverse device effect is any adverse device experience, reported in this protocol, contained in a report of prior investigations, Informed Consent Form and, or general investigational plan.

A list of anticipated AEs is presented in [Appendix 1](#).

Subsequent Secondary Surgical Interventions, which are surgical interventions occurring at the index fusion site(s) subsequent to the completion of the index procedure, will be evaluated and

presented separately from other adverse events. While secondary surgical interventions will not be classified as adverse events, the reasons for these procedures may be. An explanatory description will be provided as an adverse event narrative and will include:

- the reason for each subsequent secondary surgical intervention and
- the action taken
- the types and timing of these surgeries

The following are types of secondary surgical interventions at the index fusion site along with their definitions:

- **Revision.** A procedure that adjusts or in any way modifies or removes *part* of the original implant configuration, with or without replacement of a component. A revision may also include adjusting the position of the original configuration.
- **Removal.** A procedure where *all* of the original system configuration is removed with or without replacement due to, for example, mechanical failure of the graft material, pain, or infection.
- **Reoperation.** Any surgical procedure that does not include removal, modification, or addition of any components to the system (e.g., drainage of a hematoma at the surgical site).
- **Supplemental fixation.** A procedure in which additional instrumentation not under study in the protocol is implanted.

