### **1.3 Benefit / Risk Aspects**

Arthrodesis remains the most common surgical procedure for patients with debilitating ankle and hindfoot arthritis. Average nonunion rates remain high (10-15%) but can be substantially higher in patients with co-morbid factors such as diabetes and other metabolic diseases, obesity, smoking, age  $\geq 65$  and osteoporosis. The data with both ABG and bone graft replacement products, particularly in light of their nearly ubiquitous use in this setting and the apparent equivalence of their fusion rates, suggest that a major differentiator is the lack of pain, dysfunction and morbidity related to graft donor sites when bone graft replacement products are utilized.

The inclusion of patient reported outcomes, functional evaluations and quality of life assessments is therefore important in evaluating the differences between these approaches. The current clinical trial was designed with this in mind, incorporating both radiologic assessment of fusion rate and validated scales to assess pain and functional outcome.

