### **2.2.3 Safety Endpoints**

The safety endpoints are as follows:

- Frequency, severity and seriousness of Adverse Events (AEs)
- Device or Procedure Related SAEs
- Secondary surgical intervention including revision, removal, reoperation or supplemental fixation
- Subsidence, device migration, nonunion, osteolysis and/or heterotopic ossification in the area surrounding the implant site by radiographic assessment
- Presence of anti-B2A antibodies (Ab) in serum

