### 9.7.3 Other Safety Variables

Descriptive statistics of subsidence, device migration, nonunion, osteolysis and/or heterotopic ossification in the area surrounding the implant site by radiographic assessment, clinical laboratory testing and antibody monitoring will be presented for the safety analysis set by treatment group.

Number and percentage of subjects reporting the following events will be summarized:

- Any secondary surgical interventions including revisions, removals, reoperations, or supplemental fixations
- Secondary surgical intervention related to the graft material including revisions, removals, reoperations, or supplemental fixations

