- Ectopic bone growth (bone forming outside of normal bone growth areas)
- Abnormal cell growth (growth of tissue or cells beyond the norm)
- Negative effects on pregnancy or fetus
- Immune response (bodily response against foreign material)
- Significant increase in liver enzyme measures

Adverse events associated with harvesting autologous bone graft include:

- pain at the graft harvest site (evaluated as an efficacy assessment, not reported as an AE)
- swelling
- fracture at the graft harvest site
- soft tissue injury (swelling, warm to touch and/or pain to affected area)
- harvest site wound infection (drainage or pus at surgical site)
- cellulitis (inflammation of the soft tissue, especially below the skin characterized by fever, swelling, redness and pain)
- failure of the tissue to heal properly (wound breakdown or opening)
- other wound problem (fluid pocket formation)
- other infection (fever, aches and/or pain)
- hemorrhage (severe bleeding)
- nerve damage (weakness, tingling, and or numbness)
- muscular damage
- phlebitis thromboembolus (swelling, pain and/or redness at affected area)

**Appendix 2 Foot and Ankle Ability Measure Activities of Daily Living (FAAM-ADL)  
Questionnaire**

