1.1 Definitions/ Abbreviations

1.1.1 Definition of Terms

Terms	Definitions
Screened	Signed the informed consent form
Screen failed	Discontinued from the trial prior to randomization
Device	AMPLEX or ABG
Procedure	Index surgical fusion procedure or bone graft harvest procedure

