10.3 Secondary Surgical Intervention

Numbers and percentages of subjects who required any secondary surgical interventions as well as each type of the secondary surgical intervention (revision, removal, reoperation, or supplemental fixation) will be summarized.

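### The secondary-surgery tables cover the index fusion site only, so no planned output counts operations at the bone-harvest site, which only ABG subjects have

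*Protocol*

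**What the plan says.** **Definition.** Protocol 8.1 limits secondary surgical interventions to "surgical interventions occurring at the index fusion site(s) subsequent to the completion of the index procedure". It repeats the limit when it introduces revision, removal, reoperation and supplemental fixation: "The following are types of secondary surgical interventions at the index fusion site along with their definitions".

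**Endpoint and tables.** The safety endpoint in protocol 2.2.3 names no site: "Secondary surgical intervention including revision, removal, reoperation or supplemental fixation". Nor does the row planned in protocol 9.7.3: "Any secondary surgical interventions including revisions, removals, reoperations, or supplemental fixations". SAP 10.3 plans "Numbers and percentages of subjects who required any secondary surgical interventions as well as each type of the secondary surgical intervention". The SAP gives no definition of its own, so the one in protocol 8.1 carries through.

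**Harvest elsewhere in the plan.** For attributing events, harvest is part of the study procedure. SAP 1.1.1 defines the procedure as "Index surgical fusion procedure or bone graft harvest procedure", and protocol 8.2.3 and SAP 10.2 treat procedure-related events the same way. Protocol 7.2.2.4 confirms that AMPLEX subjects have no harvest. Protocol Appendix 1 lists anticipated harvest complications that include fracture, hemorrhage and "harvest site wound infection (drainage or pus at surgical site").

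**The concern.** ABG subjects have two operated sites and AMPLEX subjects one, but repeat surgery is counted at one site in both arms. A reader of a row headed as any secondary surgery is likely to take it as the total, and under protocol 8.1 it is not.

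This matters because the case for the device leans on avoiding harvest. Protocol 1.3 says that "a major differentiator is the lack of pain, dysfunction and morbidity related to graft donor sites" when graft substitutes are used. Protocol 9.1 defends the -12% margin partly by the benefit of removing the risks of ABG. A return to theatre for the donor site is a direct measure of that risk, and the plan has no line for it.

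The wording also leaves room for uneven classification. The example given for a reoperation in protocol 8.1 is drainage of a hematoma at the surgical site, and Appendix 1 uses the term surgical site when it describes a harvest-site infection. With up to 50 centers, similar harvest-site drainages could be recorded differently.

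**Working it through.** **1. Where a harvest-site operation would appear**

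| Planned output | Covers the harvest site? |
|---|---|
| Secondary surgery, any and by type (protocol 9.7.3, SAP 10.3) | No, by the definition in protocol 8.1 |
| AEs leading to secondary surgery (SAP 10.2.1, 10.2.2) | No, same defined term |
| Narrative of reason, action, type and timing (protocol 8.1) | No, index-site operations only |
| Procedure-related AEs and SAEs (protocol 9.7.2, SAP 10.2.1, 10.2.2) | The cause, yes; fusion and harvest are pooled and the operation is not counted |
| Primary composite, related-SAE component | Only if the cause is a related SAE by Week 52 |
| Primary composite, component on interventions to promote fusion | No, unless the operation was meant to promote fusion |

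SAP 10.2 has relatedness to the fusion procedure and to the harvest procedure evaluated separately, but no planned table reports them separately.

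**2. Arm sizes**

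The documents give no re-operation rate to reproduce. The design figure behind the arm sizes does reproduce. The inputs from protocol 9.1 are 60% and 62% success, a 12-point margin, one-sided 5%, 85% power and 2:1 allocation:

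n(ABG) = (1.645 + 1.036)² × [0.60 × 0.40 + (0.62 × 0.38)/2] / (0.62 − 0.60 + 0.12)² = 7.19 × 0.3578 / 0.0196 = 131.2, rounded up to 132.

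The total is 3 × 132 = 396, as stated. Allowing for 15% loss gives 396/0.85 = 466, and 480 are planned, 160 of them ABG.

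**3. Possible size of the omission**

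Let h be the proportion of ABG subjects who have a harvest-site operation. This is an assumption. The upper end is the 5.5% complication rate for tibial graft sites in protocol 1.1, as if every such complication led to surgery. The lower end is 0.

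- Expected uncounted ABG subjects = 160 × h
- Chance of at least one = 1 − (1 − h)^160
- Any-site ABG rate = 1 − (1 − 0.05)(1 − h), taking an index-site rate of 5% for illustration (not in the documents) and independence between sites

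| h | Uncounted of 160 | Chance of at least one | Any-site ABG rate |
|---|---|---|---|
| 0% | 0 | 0 | 5.0% |
| 1% | 1.6 | 0.80 | 6.0% |
| 2% | 3.2 | 0.96 | 6.9% |
| 5.5% | 8.8 | above 0.99 | 10.2% |

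For AMPLEX as treated, the uncounted number is 0 throughout.

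**The case against.** The endpoint is openly an index-site measure. Three of its four types concern the implant configuration or added instrumentation, and protocol 9.7.3 adds a row for interventions related to the graft material. Judged by that purpose, it is correct.

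Most of the substance is also captured elsewhere. Protocol 8.1 makes the reason for any surgical procedure an AE. Events possibly related to harvest go to the CEC as procedural events (protocol 3.3.1, SAP 10.2) and enter the procedure-related tables. Protocol 3.4.2 assigns the benefit/risk assessment to the composite, which already includes harvest-site pain and procedure-related SAEs. Safety endpoints are only summarized descriptively, and leaving these operations out of the table favors ABG, so it cannot flatter the device.

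All of this stands, and it keeps the point small. It does not supply the missing count. A pooled procedure-related row does not show which events came from the harvest site or which led to an operation. The composite misses an operation whose cause is not classed as a related SAE, which without hospitalization can turn on medical judgment. It also misses anything after Week 52, although follow-up runs to Week 78.

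**Conclusion.** The point holds as a low-severity gap in reporting. A stated definition leaves one arm's second operated site out of the secondary-surgery tables, and nothing else in the plan counts those operations or gives an any-site rate. The size is 0 to about 9 of 160 ABG subjects. This rests on the assumed range of 0% to 5.5% and on the planned arm size; the actual as-treated number may differ.

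Three stronger readings are tempting and are not supported:

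- **That the ABG re-operation rate is understated.** The index-site rate is not. Only an any-site rate would fall short, and only if harvest-site operations occur.
- **That harvest-site events are lost or the main result is biased.** Their causes are recorded, adjudicated and tabulated, and related SAEs by Week 52 count against the primary endpoint. The secondary-surgery table is not tested, so type I error and power do not change.
- **That a known share of ABG repeat surgery goes uncounted.** This would need an index-site rate and the fraction of harvest complications that require surgery. The documents give neither. The 5.5% covers tibial sites only, while calcaneus and iliac crest are also allowed, and it includes events as mild as seroma and paresthesia.

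**What to change.** Leave the index-site definition and its four types as they are. Then:

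- Label the SAP 10.3 table *index site only*, and say the same in protocol 9.7.3.
- Add two rows to it, by arm as treated: *surgery at the bone-harvest site* and *any secondary surgery at the index or harvest site*.
- Add a matching line in SAP 10.2.1 and 10.2.2 for AEs leading to harvest-site surgery.
- Record the site of each operation, if the eCRF (which is not among the documents) does not already do so. This is best settled early, because later recovery would depend on free text.

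No new adjudication route is needed for the underlying events, since potential procedure-related AEs already go to the CEC. The cost is a few table rows and one data item. The downside is one further descriptive safety count to interpret, probably on small numbers.

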## 8.2 Collection and Recording of Adverse Events

### 8.2.1 Collection of Adverse Events

The Investigator must monitor the condition of the subject throughout the trial from the time of informed consent until the last visit.

The sources of adverse events include:

- The subject's response to questions about his/her health (a standard non-leading question such as "How have you been feeling since your last visit?" is asked at each visit)
- Symptoms spontaneously reported by the subject
- Investigations and examinations where the findings are assessed by the Investigator to be clinically significant changes or abnormalities
- Other information relating to the subject's health becoming known to the Investigator (e.g., hospitalization)

### 8.2.2 Recording of Adverse Events

All adverse events will be coded by system organ class and preferred term using the Medical Dictionary for Regulatory Activities (MedDRA) (version effective at trial start).

During each clinical follow-up, the Investigator or Investigator designee will determine AE occurrences. Each adverse event is considered to be either anticipated or unanticipated as described above. The site is required to report all adverse events that occur during the trial. AEs will be collected from the time of informed consent until the final follow up.

Post-treatment outcomes that are evaluated as efficacy endpoints, such as pain on weight-bearing, harvest site pain, etc., will not be reported as AEs. Post-operative pain is, in general, anticipated, typically improves over time, and it will not be considered an AE. However, surgical site pain that is associated with a complication, or worsens over time, may be considered an AE.

Any abnormal laboratory test results or other safety assessments (e.g., vital signs measurements, etc.) considered to be clinically significant in the medical and scientific judgment of the Investigator are to be recorded as AEs.

The sign and symptoms and/or clinical sequelae resulting from lack of efficacy will be reported if they fulfill the definition of an AE or SAE.

Internal fixation medical devices (e.g., screws, plates, pins and staples) are being used in this study and are considered ancillary devices. Medical device events associated with these ancillary devices, including those resulting from screw loosening or malfunctions of the ancillary device, must be documented and reported as adverse events by the Investigator throughout the study.

### 8.2.3 Assessment of Adverse Events

**AE Severity:** All AEs will be assessed for severity (see table below). Note: the term “severe” is a measure of intensity and that a severe AE is not necessarily serious.

**Table 5 AE Severity Grading Scale**

Severity Grade	Description
Mild (1)	Transient or mild discomfort; no limitation in activity; no medical intervention or therapy required. The subject may be aware of the sign or symptom but tolerates it reasonably well.
Moderate (2)	Moderate limitation in activity, minimal medical intervention/therapy required.
Severe (3)	Marked limitation in activity, medical intervention/therapy required hospitalizations possible.

**Device Related Adverse Event:** Relationship to the graft material will be assigned *one* of the following:

- **Definitely:** Clear evidence event caused by graft material; strong temporal relationship and an alternative cause is unlikely.

- **Probably:** Reasonable probability event might be caused by graft material. The event has a temporal relationship to the study procedure(s), and follows a known pattern of response and an alternative cause seems unlikely.
- **Possibly:** Reasonable possibility event is caused by graft material. The event has a temporal relationship to the study procedure(s) and follows a known pattern of response, but a potential alternative cause may be present.
- **Unlikely:** Evidence that there may be other causes and the relationship to the graft material, although cannot be completely ruled out, is remote.
- **Unrelated:** Cause of the event is known and the event is in no way related to any aspect of the graft material.
- **Unknown:** Causality cannot be determined.

The causality of AEs will be determined by the Investigator, and the CEC will adjudicate it.

In addition to the graft material, the relationship to the following will also be determined for each AE, if possible:

- **Ancillary Device Adverse Event:** An adverse event which is determined to be a consequence of an ancillary device and is not specifically related to the use of graft material, but could be related to the placement of the graft material. An ancillary device is defined as an approved medical device used in conjunction with the graft material, and used during the study procedure (e.g., internal fixation screws, etc.)
- **Procedure-Related Adverse Event:** An adverse event which is determined to be a consequence of the arthrodesis or harvest procedure and is not specifically related to use of the graft material or ancillary devices, but could be related to the placement of the graft material or ancillary devices.

Every effort should be made to assess the causality of all events. If the causality cannot be determined, it should be classified as unknown. Events classified as “unknown” causality will be considered related for reporting purposes.

